Notes: Circles indicate MARVEL subjects classified as having intact AV node conduction. Squares indicate MARVEL subjects having persistent 3rd degree AV block.

The sinus node function will be determined based upon the duration of the P-P intervals during both the atrial sensing setup and subsequent VDD mode operation during implant and both the VDD and VDI resting phases at the 1-month and 3-month follow-up visits. P-P intervals greater than the lower rate interval (i.e., 1200 ms at a lower rate of 50 bpm), or P-P intervals less than 600 ms (corresponding to a sinus rate > 100 bpm) will be identified. If these long or short intervals comprise less than 5% of the total P-P intervals during these two procedure steps, then the subject will be classified as having normal sinus node function. If these long or short intervals comprise 5% or more of the P-P intervals, then the ECG will be manually reviewed to classify the subject as having normal sinus node function or sinus node dysfunction. A manual review may also be triggered if the subject has been identified during the study as having an atrial arrhythmia, such as atrial flutter or atrial fibrillation, where the P-waves may not have been identified during the P-wave truthing process.

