7.9.2.4 Ventricular Event Spreadsheet

Holter datasets will be further analyzed to extract information related to ventricular sensing (including V-V interval). Specifically, a Matlab program will collate each ventricular event, times corresponding to distinct study procedures, and other device markers and information in a .csv file, referred to below as an “VEvent spreadsheet” that will contain one row per ventricular event (i.e., ventricular pace or sense). This contrasts with the accuracy spreadsheet where each row contains information for a P-wave.

Similar to the discussion of the accuracy spreadsheet creation, loss of communication between the Holter and the implanted Micra AV, called telemetry dropout, can lead to loss of the Micra and Micra AV supplemental markers. Note that since this spreadsheet is created from ventricular pacing markers, the loss of a pacing marker can only be inferred from a long interval between ventricular events with evidence of telemetry dropout. Some analyses may rely on Micra AV pacing and supplemental markers from the previous pacing cycle. The times of the preceding markers are provided in the spreadsheet, and if these exceed the previous V-V interval, telemetry dropout is implied.

Figure 7 shows an example VEvent spreadsheet. The VEvent spreadsheet uses the ventricular event as the fiducial marker and contains one record per ventricular event that occurred during the Holter recording. The columns of the VEvent spreadsheet are defined below:

1. (A): Time of ventricular event in seconds relative to the beginning of the Holter recording
2. (B): Marker code associated with the ventricular event. Codes of 160, 172, or 173 mean a VS and codes of 163 or 164 mean a VP
3. (C): Programmed lower rate in bpm
4. (D): Time in seconds from the ventricular supplemental marker prior to the V-Event to the V-Event. The Micra AV algorithm mode and pacing mode are derived from the ventricular supplemental marker. The ventricular supplemental marker is uplinked separately after each V-Event
5. (E): Micra AV algorithm mode at last supplemental marker before the current V-Event (1=VDD/Adaptive, 3=VDI/Monitor)
6. (F): Pacing mode at last supplemental marker before the current V-Event (0=OOO, 1=VOO, 2=VVI, 3=OVO, 4=ODO, 5=VDI, 6=VDD, 10=VVIR, 13=VDIR, 130=VVI40)

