7.9.3.3 Analysis Methods

At the 1-month study visit, a Holter monitor will be placed on the subject. Each subject's Holter monitor will record surface ECG and Micra AV markers. Specifically, the Holter will record whether the Micra AV senses an atrial contraction (A4 signal representing active ventricular filling detected by the accelerometer), delivers a pacing spike, or inhibits a pacing spike based on a sensed intrinsic R-wave. Holter files will be processed as described in Section 7.9.2.

The accuracy spreadsheet derived from each Holter file (see section 7.9.2.3) will be used to determine the synchrony status (yes or no) for each P-wave. Each accuracy spreadsheet will be imported into SAS

and/or R and the P-P interval computed for each P wave i (where $i > 1$) as the time in seconds in Column 1 (A) for the i^{th} P-wave minus the time in seconds in Column 1 (A) for the $i^{th}-1$ P-wave. Each P-wave in the accuracy spreadsheet file will be classified as being evaluable or not evaluable. P-waves that are not evaluable include:

1. P-waves with no ventricular sense or pace markers and indication of telemetry dropout in the first 300 ms after the P-wave. These are identified from the accuracy spreadsheet where column 13 (M) = 0 and column 14 (N) = 1.
2. P-waves that occur during an AV conduction mode switch for subjects with a predominant rhythm of persistent 3rd degree AV block and normal sinus node function. During an AV conduction mode switch the pacing mode is set temporarily to VVI40 while the device checks for intrinsic AV conduction. These are identified from the accuracy spreadsheet where a supplemental marker in the preceding P-P interval (column 15 (O) < P-P interval), and the pacing mode in the supplemental marker is VVI40, indicating a mode switch (column 17 (Q) = 130). Note that for the pacing mode, the supplemental marker indicates the pacing mode on the next ventricular event, which is why a look-back to the preceding supplemental marker is necessary to determine if the current ventricular event is in a mode-switched state.

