3. P-waves that occur during VVI mode during the resting and ambulatory periods for subjects with a predominant rhythm of persistent 3rd degree AV block and normal sinus node function. The device may be permanently programmed to VVI or switches to VVI mode temporarily each hour to perform a pacing threshold confirmation check and once per day to perform a pacing capture threshold test. While the device is in VVI mode AV synchronous pacing is not expected to occur in these subjects. These cycles are identified from the accuracy spreadsheet where a supplemental marker in the preceding P-P interval (column 15 (O) < P-P interval), and the pacing mode in the supplemental marker is VVI40, indicating a mode switch (column 17 (Q) = 2).

All other P-waves in the accuracy spreadsheet will be considered evaluable. Evaluable P-waves will be considered synchronous if they occur within 300 ms of the following ventricular event. Thus, evaluable P-waves will be considered synchronous if column 2 (B) ≤ 0.3 and asynchronous if column 2 (B) > 0.3 .

For the analysis of the primary objective, P-waves with records in the accuracy spreadsheet for each subject's 1-month Holter file corresponding to resting period (i.e., columns 11 (K) and 12 (L) indicate resting phase) will be selected.

A logistic regression model using generalized estimating equations, to account for the fact that the Micra AV's performance may be correlated within a study subject, will be used to construct a single estimate of the rate of AV synchrony and its 95% two-sided confidence interval across all subjects. Specifically, the outcome variable will be each successful/unsuccessful synchronous beat during the approximately 20 minutes resting period at the 1-month visit and the model will contain an intercept

term and consider observations repeated across subjects with an exchangeable working correlation structure.

A sample SAS PROC GENMOD statement for computing the overall point estimate for the algorithm's ability to provide AV synchrony and its two-sided confidence interval across all subjects is displayed below:

```
proc genmod data = AVsynchData descending;
  class pt;
  model AVsynch = / dist = binomial link = logit;
  repeated subject = pt / type = exch;
  estimate 'probability of success' int 1/ alpha = 0.05;
  output out = pred p = phat;
run;
```

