7.9.4.3 Analysis Methods

A Holter monitor will be placed on each subject at the 1-month and 3-month visits. Each Holter file will be processed as described in section 7.9.2 and the AV synchrony during the 20-minutes resting periods at the 1-month and 3-months visits will be compared using a generalized linear model incorporating generalized estimating equations. The response for this model on an individual heartbeat basis will be AV synchrony endpoint met as defined in section 7.9.3.1 (i.e., 1= yes, 0= no). The model will also incorporate an intercept term and indicator for visit (1-month or 3-month visits) and utilize an exchangeable working correlation structure to account for the fact that the atrioventricular synchrony may be correlated within subject. The difference in the least squared means between visits on the linear scale (i.e., when utilizing the identity link function with the binomial distribution) and its related 95% confidence interval will be used to assess the stability of the AV synchronous pacing rate between study visits.

A sample SAS PROC GENMOD statement for comparing the percentage of AV synchronous pacing between study visits is displayed below:

```
proc genmod data = AVsynchData descending;
  class pt visit;
  model AVsynch = visit / dist = binomial link = id;
  repeated subject = pt / type = exch;
  lsmeans visit / cl;
  estimate 'Difference' visit -1 1/ alpha = 0.05;
run;
```

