7.9.5.3 Analysis Methods

At the 1-month visit, a Holter monitor will be placed on the subject and following the in-clinic study procedures the subject will wear the Holter monitor for approximately 24 hours as they go about their activities of daily living. The Holter files will be processed as described in section 7.9.2. A logistic regression model using generalized estimating equations will be used to construct a single estimate and 95% confidence interval for algorithm performance across all subjects using the methods described in section 7.9.3.3. For analysis purposes, the ambulatory period will be defined as starting at the end of the 20-minute resting period.

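### SAP 7.9.3.3 rules 2 and 3 look back one P-P interval for a mode marker sent once per ventricular beat, so some VVI40 and VVI P-waves stay evaluable with no marker lost (effect probably small)

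*SAP*

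**What the plan says.** SAP 7.9.3.3 lists three kinds of non-evaluable P-wave. Rule 1 covers telemetry dropout. Rules 2 and 3 apply to subjects with persistent 3rd degree AV block and normal sinus node function. They cover the VVI40 conduction check, and VVI (hourly and daily threshold tests, or permanent programming).

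Rule 2 gives this column test: "These are identified from the accuracy spreadsheet where a supplemental marker in the preceding P-P interval (column 15 (O) < P-P interval", with pacing mode code 130. Rule 3 repeats the age condition and ends "and the pacing mode in the supplemental marker is VVI40, indicating a mode switch (column 17 (Q) = 2". The default follows: "All other P-waves in the accuracy spreadsheet will be considered evaluable".

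The column D note in SAP 7.9.2.4 gives the marker's timing: "The ventricular supplemental marker is uplinked separately after each V-Event". SAP 7.9.1 and 7.9.2.3 read a marker older than the P-P interval as lost to dropout. For its own spreadsheet, 7.9.2.4 compares marker age with the V-V interval instead.

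Secondary objective #2 uses the same rules, since its estimate is made "for algorithm performance across all subjects using the methods described in section 7.9.3.3".

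**The concern.** The window is atrial but the marker is ventricular. If the ventricle beats more slowly than the atrium, P-waves outnumber markers, so some P-P intervals contain no marker even with perfect telemetry. Such a P-wave fails the age condition, is not excluded, and becomes evaluable by default.

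This situation is expected in the primary cohort. SAP 7.1.4 counts "P-P intervals greater than the lower rate interval (i.e., 1200 ms at a lower rate of 50 bpm" as long, and intervals under 600 ms as short. "If these long or short intervals comprise less than 5% of the total P-P intervals during these two procedure steps", sinus function is normal without manual review. In those subjects more than 95% of P-P intervals lie between 600 and 1200 ms at a lower rate of 50 bpm, all shorter than a 40 bpm ventricular cycle.

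At stake is whether the pre-specified exclusion removes the beats it names, for the primary endpoint and for ambulatory synchrony. The beats kept are those latest in the ventricular cycle, and some of them count as synchronous by chance.

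**Working it through.** **Inputs.** P-P limits of 600 and 1200 ms and a lower rate of 50 bpm (SAP 7.1.4); synchrony window 300 ms (7.9.3.1); reference synchrony 89.2% and median confidence distance 2.9 points at n = 75 (7.9.3.4, Table 2). Assumptions: VVI40 paces at 40 bpm, VVI at 50 bpm, no escape beats, atrium and ventricle dissociated.

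**The SAP's own conversion.** 60000/50 = 1200 ms and 60000/100 = 600 ms, as stated. By the same formula VVI40 gives 60000/40 = 1500 ms.

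**Timing premise checked on Figure 6.** At row 12369, P-P = 8335.739 - 8335.050 = 0.689 s and O = 0.703 s, with dropout flags 0 on that row and the one before. The marker is older than one P-P interval, so the SAP would call it lost. Figure 7 shows that it was received: event at 8335.953 minus 0.917 = 8335.036 s, which equals 8335.739 - 0.703. Two P-waves simply fell in one ventricular cycle. Of the 23 rows whose preceding row has I = N = 0, 7 have O > P-P and one more ties.

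**Share kept and chance synchrony.** With dissociation, marker age at a P-wave is uniform on 0 to VV.

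- Share kept: s = 1 - PP/VV.
- Synchronous among those kept: q = min(1, 0.3/(VV - PP)).
- Shift against full exclusion, if a fraction f of P-waves is in the mode: f·s·(q - 0.892)/(1 - f + f·s).

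The time in these modes is not given, so f = 1% is assumed (12 s of a 20-minute rest, or 36 s per hour), equal across subjects.

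| P-P (sinus rate) | VVI40: s | q | shift, points | VVI at 50: s | q | shift, points |
|---|---|---|---|---|---|---|
| 600 ms (100) | 60% | 33% | -0.34 | 50% | 50% | -0.20 |
| 800 ms (75) | 47% | 43% | -0.22 | 33% | 75% | -0.05 |
| 1000 ms (60) | 33% | 60% | -0.10 | 17% | 100% | +0.02 |
| 1200 ms (50) | 20% | 100% | +0.02 | 0% | – | 0 |

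Example, VVI40 at 600 ms: 0.01 × 0.60 × (0.333 - 0.892)/(0.99 + 0.006) = -0.0034.

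Simulation of 400,000 P-waves per case (3% P-P variation, 20 ms marker delay) agrees, except that variation lowers the 100% entries to 81-93%, which brings the small positive shifts to about 0.

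**Rates from the SAP's example recording.** Mean P-P = (8353.372 - 8334.317)/27 = 0.706 s (85 bpm). Lower rate 49.87 bpm gives 1.203 s. Share kept: 1 - 0.706/1.203 = 41% in VVI and 1 - 0.706/1.5 = 53% in VVI40. Shifts per 1%: -0.12 and -0.27 points.

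**Escape rhythm.** At 45 bpm (V-V 1.333 s) during VVI40 and sinus 75, the share falls from 47% to 1 - 0.8/1.333 = 40%.

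**Corner case for secondary objective #2.** One of 75 equally weighted subjects in VVI at 50 bpm throughout, sinus 75, with 89.2% as reference: (0.75 - 0.892)/75 = -0.2 points.

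**The case against.** Four points can be made against this.

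- **Intent is clear.** Rules 2 and 3 open by naming all P-waves in those modes; only the column test is narrower. The program is not visible, so the beats are kept only if that test is coded literally. This stands, but the column test is the operational definition and should match the intent.
- **The episodes are mostly short.** The shares are averages. If the episode starts at a random phase, the average does not depend on its length, but a single short run may contain no affected P-wave. A reader might infer that every run with V-V longer than P-P leaks beats; the documents do not support that.
- **The effect is small and rests on unstated inputs.** This stands. Protocol 8.9.8 records rest in VDD, there is no performance requirement, and the shift is mostly downward. If VVI paces at or above the sinus rate, rule 3 misses almost nothing.
- **Figure 6 contains no VVI beats.** A reader might take it as showing misclassified beats. Every row is VDD, so it shows only that a marker can be older than one P-P interval without flagged dropout.

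A reader might also extend the point to secondary objective #1. Its methods say "Each Holter file will be processed as described in section 7.9.2 and the AV synchrony during the 20-minutes resting periods" and refer to 7.9.3.1 for the endpoint, without citing 7.9.3.3. Use of rules 2 and 3 there is only implied.

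**Conclusion.** The point holds as a minor defect in the column test. As written, rules 2 and 3 do not remove all the beats they are meant to remove when the ventricle is paced more slowly than the sinus rate. That is expected in VVI40, and in VVI only if it paces below the sinus rate. The timing argument follows from the SAP's text and is firm.

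The size is not firm. Steady-state shares kept are 20-60% (VVI40) and 0-50% (VVI at an assumed 50 bpm) over sinus 50 to 100 bpm. The shift of about 0 to -0.34 points per 1% of P-waves rests on an assumed time in mode. A reader might infer a materially biased primary result; nothing in the documents supports that. A recording left in VVI for the whole ambulatory period, which rule 3 allows for, is a corner case for secondary objective #2.

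Separately, rule 3 names VVI40 but gives code 2. The column Q key in 7.9.2.3 defines 2 as VVI and 130 as VVI40. Rule 3's opening shows that VVI is meant, so this is a wording error.

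**What to change.** In rules 2 and 3, replace the condition O < P-P with a ventricular look-back:

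1. Use column Q when the marker belongs to the preceding ventricular event (O ≤ F) and no telemetry dropout occurred since that marker. Both parts are needed. Figure 6 row 12385 has O = 1.447 ≤ F = 1.461, yet its V-V of 2.108 s with flagged dropout exceeds the 1.203 s lower-rate interval, so a ventricular event was probably lost. Take dropout timing from the Holter or ventricular event data, because columns I and J give no start time.
2. If the P-wave falls between a ventricular event and its marker (O > F and R < B), take the mode from column F of the ventricular event spreadsheet for the event at time A + B, as the only lookup. Row 12371 is an example: 8337.128 + 0.947 = 8338.075, row 8932 in Figure 7. Without this step a 20 ms marker delay leaves 1.3-1.7% of these P-waves in (20/1500 to 20/1200).
3. State how P-waves with dropout since the last marker are treated.
4. Correct rule 3 to read that the pacing mode is VVI (Q = 2).

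Two wording items go with this: say in 7.9.4 whether rules 2 and 3 apply, and align the dropout notes in 7.9.1 and 7.9.2.3 with the V-V comparison in 7.9.2.4.

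The cost is a revised condition, one lookup, dropout timing carried into the analysis file, revalidation at the level that SAP section 8 sets for primary-objective programs, and a few words of SAP text. No new data are needed.

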7.9.3.4 Sample Size

The MARVEL 2 study reported an average AV synchrony rate during rest of 89.2% (95% CI: 84.8% - 92.5%) with a median of 94.3% across the 40 subjects with a predominant heart rhythm of 3rd degree AV block and normal sinus node function and P-waves visible on their Holter ECG channel. The remaining subjects included 17 subjects with intact AV conduction, and 7 subjects with other predominant rhythms. Based on the distribution of predominant rhythms in the MARVEL 2 study together with the enrollment strategy described in section 5, it is expected that approximately half of the subjects with usable Holter recordings will have a predominant rhythm of 3rd degree AV block and normal sinus node function at their 1-month visit.

A simulation based on resampling with replacement from the MARVEL 2 subjects suggests that a sample size of 75 subjects with Holter recordings and with a predominant rhythm of 3rd degree persistent AV block and normal sinus node function at the 1-month visit will enable the percentage of AV synchrony to be measured with a precision (distance from point estimate to lower 2-sided 95% confidence interval) of <3.5% with 89.7% probability. Since it is expected that approximately half of the subjects with usable Holter data at the 1-month visit will have a predominant rhythm of persistent 3rd degree AV block and normal sinus node function, approximately 150 subjects with usable Holter files will be required to evaluate the primary objective. To account for the possibility of unusable Holter recordings,

unsuccessful Micra AV implant attempts, and study attrition, approximately 175 subjects may be enrolled.

Since the number of subjects that will have a predominant rhythm of 3rd degree AV block at the 1-month visit is somewhat unknown, Table 2 displays the relationship between the number of subjects that will contribute to the primary efficacy analysis and the distance between the point estimate and lower 95% confidence interval for sample sizes ranging from 40 to 90 subjects.

Table 2: Relationship Between Sample Size and Confidence Interval Width

n ¹	Median Point Estimate (%) ²	Median Lower 95% CI	Median Distance from Point Estimate to Lower CI	Probability Distance <3.5%
40	88.76%	84.83%	4.1%	37.7%
50	88.73%	85.19%	3.5%	45.2%
60	88.79%	85.58%	3.2%	63.0%
70	88.82%	85.90%	2.9%	81.9%
75	88.76%	85.87%	2.9%	89.7%
80	88.73%	85.96%	2.8%	92.9%
90	88.76%	86.13%	2.6%	98.6%

¹n is the number of subjects with usable Holter files with a predominant rhythm of persistent 3rd AV block and normal sinus node function at the 1-month visit.

²Based on 1000 bootstrap samples from 40 subjects in the MARVEL 2 study with a predominant rhythm of persistent 3rd AV block and normal sinus node function during Holter monitoring.

Program Name: V:\AccelAV\Sample_Size\AccelAV_ciWidth.R

7.9.3.5 Determination of Subjects and Data for Analysis

All enrolled subjects with usable Holter data, a predominant rhythm of persistent 3rd degree AV block and normal sinus node function at the 1-month visit, and at least 500 evaluable beats during the resting period at the 1-month visit will be included. Specifically, data from the approximately 20 minute resting period at the 1-month visit will be included in the analysis of the primary objective.

7.9.3.6 Missing Data

Given the relatively short duration of the study, missing data is not expected to be a serious issue. However, missing data may occur if the Holter telemetry signal is lost or the Holter data file is otherwise corrupted (i.e., Holter file is not considered usable).

Since telemetry dropout may influence the number of evaluable beats, the total number of heart beats and total number of evaluable beats will be summarized.

If any subjects do not have usable Holter data during the study, the reason the Holter data was not usable will be discussed.

Additionally, a sensitivity analysis will be performed to assess the sensitivity of the observed AV synchrony percentage estimate with respect to the missing data. The analysis will consist of including in the statistical model all subjects that had some usable Holter data during the 20-minutes resting period at the 1-month visit regardless of the number of evaluable beats. Other stochastic based methods to investigate the sensitivity of the results to the number of unevaluable beats due to telemetry lost may be utilized if necessary.

7.9.3.7 Other Planned Analyses

As described in section 7.1.4, subjects may have different predominant heart rhythms at their 1-month and 3-month visits. For example, a subject may have intact AV conduction at their 1-month visit but have persistent 3rd degree AV block and normal sinus node function at their 3-month visit. Thus, for subjects with different predominant heart rhythms at their 1-month and 3-month visits, an estimate of percent AV synchrony will also be computed using the methods described in section 7.9.3.3 using each subject's first visit Holter recording where they have at least 500 evaluable beats and have a predominant rhythm of persistent 3rd degree AV block and normal sinus node function.

The AV synchrony percentage will also be computed using the methods described in section 7.9.3.3 for subjects not included in the primary objective analysis cohort including those subjects with intact AV conduction and other predominant rhythms.

The AV synchrony percentage during rest will also be computed using the methods described in section 7.9.3.3 among the subset of subjects with normal sinus function at 1-month with >40% ventricular pacing during the resting period regardless of AV conduction status.

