### **12.4. Classification of Predominant Heart Rhythm During Holter Monitoring**

Holter data from the VDI data collection period and resting period will be used to determine each subject's predominant heart rhythm. Specifically, both the sinus function and AV block status will be assessed. The AV conduction status will be categorized as persistent 3rd degree AV block, intact AV conduction, or other (e.g. 1st or 2nd degree AV block). The sinus node function will be categorized as normal sinus node function, sinus node dysfunction (sinus bradycardia, sinus tachycardia, or other) or atrial arrhythmia.

A subject's 1-month and 3-month visit Holter will be assessed individually for predominant rhythm classification. Thus, a subject may have different predominant rhythms at each study visit (e.g., 3rd

degree persistent AV block with normal sinus node function at the 1-month visit, but intact AV conduction at the 3-month visit).

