### **12.5.7. Other Planned Analyses**

As described in section 12.3 subjects may have different predominant heart rhythms at their 1-month and 3-month visits. For example, a subject may have intact AV conduction at their 1-month visit but have persistent 3rd degree AV block and normal sinus node function at their 3-month visit. Thus, an estimate of percent AV synchrony will also be computed using the methods described in section 12.5.3 using each subject's 3-month visit Holter recording where they have at least 500 evaluable beats and have a predominant rhythm of persistent 3rd degree AV block and normal sinus node function.

The AV synchrony percentage will also be computed using the methods described in section 12.5.3 for subjects not included in the primary objective analysis cohort including those subjects with intact AV conduction and other predominant rhythms.

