7.9.4.4 Determination of Subjects and Data for Analysis

All subjects with persistent 3rd degree AVB and normal sinus node function and at least 500 evaluable beats during the approximately 20-minute resting period at both the 1-month and 3-month visits will be included in the analysis of this objective.

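### SAP 7.9.3.7 turns the protocol's 3-month AV synchrony estimate into a mixed-visit estimate in subjects whose rhythm changed, so no readable analysis covers the whole cohort that qualifies at 3 months

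*SAP*

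**What the plan says.** Both documents accept that rhythm can change between visits. Protocol 12.4 states: "A subject's 1-month and 3-month visit Holter will be assessed individually for predominant rhythm classification".

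Protocol 12.5.7 responds with an extra estimate by the primary method, "using each subject's 3-month visit Holter recording where they have at least 500 evaluable beats" and show the target rhythm (persistent third-degree AV block with normal sinus node function). It does not require the rhythm to have changed.

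SAP 7.9.3.7 repeats the rationale and the example, then plans something different: "for subjects with different predominant heart rhythms at their 1-month and 3-month visits, an estimate of percent AV synchrony will also be computed", and does so "using each subject's first visit Holter recording where they have at least 500 evaluable beats" with the target rhythm.

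The rest of the readable SAP treats the visits as follows.
- The primary analysis (7.9.3.3) selects "P-waves with records in the accuracy spreadsheet for each subject's 1-month Holter file corresponding to resting period", so it is a 1-month analysis only.
- Secondary objective #1 (7.9.4.3) requests "lsmeans visit / cl", which returns a mean with confidence limits for each visit, including the 3-month visit.
- Its cohort (7.9.4.4) needs the target rhythm and "at least 500 evaluable beats during the approximately 20-minute resting period at both the 1-month and 3-month visits".
- Its sensitivity analysis (7.9.4.5) lowers the beat requirement to one evaluable cycle but keeps the rhythm requirement.

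**The concern.** The protocol's analysis answers a plain question: among subjects in the target rhythm at 3 months, how good is resting synchrony? The SAP's version answers a different one. It takes only subjects whose rhythm changed, and each contributes whichever visit qualifies first. One subgroup therefore supplies 1-month data and the other 3-month data, and the pooled figure belongs to neither visit.

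Protocol 5.2 gives chronic synchrony as the study's main focus, and 3 months is the last visit. The 3-month figure that remains comes from subjects selected for a stable rhythm across both visits. If subjects newly in block at 3 months, or without a classifiable 1-month recording, behave differently, that figure will not show it.

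**Working it through.** **1. Who enters which analysis.** Here, qualifies means target rhythm with at least 500 evaluable beats at that visit.

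| 1-month status | 3-month status | Protocol 12.5.7 | SAP 7.9.3.7, first paragraph | SAP 7.9.4.4 |
|---|---|---|---|---|
| Qualifies | Qualifies | 3-month data | Not included (no change) | Both visits |
| Qualifies | Other rhythm | Not included | 1-month data | Not included |
| Other rhythm | Qualifies | 3-month data | 3-month data | Not included |
| No rhythm classification (e.g. missed visit) | Qualifies | 3-month data | Not included (no change on record) | Not included |
| Target rhythm, under 500 beats | Qualifies | 3-month data | Not included (no change) | Only in the 7.9.4.5 sensitivity analysis |

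Row 2 uses the same recording and the same criteria as the primary cohort in SAP 7.9.3.5, so those data would ordinarily have been analysed already. Rows 2 and 3 together make up the SAP's estimate. The protocol's cohort is rows 1, 3, 4 and 5, and no single readable SAP analysis covers it. Parts of the SAP are redacted, so this statement is limited to the readable text.

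**2. The plan's own precision figure.** SAP Table 2 at n = 75: 88.76 − 85.87 = 2.89 points, matching the stated 2.9. The 89.7% probability comes from bootstrapping MARVEL 2 subject-level data that the documents do not contain, so it cannot be reproduced.

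**3. Between-subject spread.** From the MARVEL 2 interval (84.8% to 92.5%, n = 40; SAP 7.9.3.4): SD ≈ (92.5 − 84.8)/(2 × 1.96) × √40 = 12.4 points. Approximate half-width = 1.96 × 12.4/√n. At n = 75 this gives 2.8, close to the table's 2.9.

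**4. Comparison of the three estimates.** The share of subjects changing rhythm is not in the documents; 5% to 15% of 75 is assumed, or about 4 to 11 subjects. The protocol cohort of 70 is also assumed.

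| Estimate | n | Half-width (points) |
|---|---|---|
| Protocol 12.5.7 | 70 | 2.9 |
| Secondary objective #1, 3-month mean | 75 − 4 = 71 to 75 − 11 = 64 (before attrition) | 2.9 to 3.0 |
| SAP 7.9.3.7 | 4 to 11 | 12.2 to 7.3 |

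The symmetric formula is too kind to small groups near the upper bound of a percentage. On the logit scale (SD 1.28, centred at 88.76%), the distance to the lower limit is 19.5 points at n = 4 and 12.3 at n = 8. For larger groups it is 3.4 at n = 70 and 3.5 at n = 65, so the similarity of the first two rows holds on either scale.

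**5. What selection could do.** With roughly equal weight per subject, leaving out a share s of the 3-month cohort whose mean differs by d points shifts the result by s × d. If s were also 5% to 15%, each point of difference would shift the result by 0.05 to 0.15 points. The documents give neither s nor d.

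**The case against.** The strongest reply is that little is lost.

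- **The 3-month visit keeps an estimate.** A reader might infer that the last follow-up point has no AV synchrony result at all. The documents do not support that. Secondary objective #1 gives a 3-month mean with limits, 7.9.4.5 relaxes the 500-beat rule, and subjects newly in block at 3 months do enter 7.9.3.7 through their 3-month recording. This stands.
- **Precision is not at stake.** On the assumptions above, the surviving half-width is practically the same as the protocol's. This stands.
- **Subjects without a good 1-month Holter are not necessarily lost everywhere.** SAP 7.1.4 has an indeterminate class for recordings without visible P-waves, which could count as a different rhythm. The second paragraph of 7.9.3.7 also covers subjects outside the primary cohort. So it would be too strong to say that no analysis can include them. But that paragraph names no visit, and the method it invokes selects the 1-month file. The gap is clear for subjects with no 1-month classification at all.
- **A both-visit cohort suits a stability objective.** It does, and Protocol 5.2 links the 3-month visit mainly to stability. That justifies 7.9.4.4; it does not explain why the separate 3-month estimate was changed.
- **The change may be documented.** A reader might infer an unexplained departure because the visible revision history does not mention it. The available history starts partway through, so its silence proves nothing. Protocol 12.1 allows non-principal changes through the SAP, and the SAP introduction promises an explanation of departures in the final report and does not limit further analyses.

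What survives is narrow: the two sections plan different estimates, and the SAP's version is neither a 3-month figure nor a figure for a natural cohort.

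**Conclusion.** The point holds as a minor one. The SAP's rule does not deliver the estimate in Protocol 12.5.7, and nothing in the readable SAP puts it back. The loss is an unselected estimate for everyone who qualifies at 3 months; it is not the 3-month result as such, and it is not precision (half-width about 3 points either way). How far selection could move the answer is unknown, because the documents give neither the rate of rhythm change nor the synchrony of those left out. The sample sizes rest on the assumed 5% to 15% and on the assumed cohort of 70. The item is listed among supplementary analyses, with no hypothesis and no performance requirement, so the primary and secondary objectives are unaffected.

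**What to change.** In SAP 7.9.3.7, restore the protocol's analysis: apply the 7.9.3.3 method to the 3-month resting recording in all subjects with persistent third-degree AV block, normal sinus node function and at least 500 evaluable beats at 3 months, whatever their 1-month rhythm or Holter status. If a first-qualifying-visit estimate is also wanted, run it in all subjects who qualify at either visit, and report how many recordings come from each.

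The cost is a wording change and one more run of existing code on Holter data the study already collects and processes. No procedure or subject is added, so this is a free improvement.
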